8.4.7 Events of Clinical Interest (ECIs)

There are no events of clinical interest for this study.

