8.4.8 Specific Events of Interest

Throughout a participant's participation in the study, new onset and/or worsening of GVHD status since Day 1 as well as relapse and progression of underlying disease (ie, the disease for which allo-HSCT was performed [see inclusion criterion 2 in Section 5.1]) will be recorded as specific events of interest. Specific events of interest are to be reported as non-serious or serious AEs as defined in Appendix 3. Standard reporting time frames for non-serious and serious AEs will apply (see [Table 4](#) in Section 8.4.1).

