9.6.2 Statistical Methods for Safety Analyses

Safety and tolerability will be assessed by clinical review of all relevant parameters separately for adults and pediatric participants including AEs and postvaccination temperature measurements.

The analysis strategy of safety parameters is summarized in Table 6. The proportion of participants with solicited injection-site AEs (redness/erythema, swelling, tenderness/pain from Day 1 to Day 5 postvaccination for adult participants, and redness/erythema, swelling, tenderness/pain, and hard lump from Day 1 to Day 14 postvaccination for pediatric participants) and solicited systemic AEs (muscle pain/myalgia, joint pain/arthritis, headache, and tiredness/fatigue from Day 1 to Day 14 postvaccination for adult participants, and muscle pain/myalgia, joint pain/arthritis, headache, tiredness/fatigue, and hives and

welts for pediatric participants) will be provided along with the corresponding within-group 95% CIs (based on the exact binomial method proposed by Clopper and Pearson [Clopper, C. J. and Pearson, E. S. 1934]). In addition, the broad AE categories consisting of the proportion of participants with any AE, a vaccine-related AE, a SAE, an AE which is both vaccine-related and serious, discontinuation due to an AE, and the proportion of participants who died will be summarized in the same manner separately for adult and pediatric participants. The proportion of participants with maximum temperature measurements meeting the Brighton Collaboration cut points (from Day 1 through Day 5 postvaccination for adult participants, and Day 1 through Day 7 for pediatric participants) will also will be provided along with the corresponding within-group 95% CIs. Point estimates by vaccination group will be provided for all other safety parameters (specific AE terms and system organ class terms).

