The analysis of safety parameters will be evaluated separately for adult and pediatric participants at 3 separate time points: (1) following administration of any of the 3 doses of V114 and Pevnar 13™ (combined across each of the vaccinations), (2) following administration of PNEUMOVAX™23 (administered 12 months after allo-HSCT), and (3) following administration of a 4th dose of V114 or Pevnar 13™ (administered 12 months after allo-HSCT). Descriptive summaries of AEs following administration of any of the 3 doses of V114 or Pevnar 13™ will include NSAE within 14 days of vaccination and SAEs/special events of interest occurring Day 1 through Month 12 after allo-HSCT (prior to vaccination with PNEUMOVAX™23 or a 4th dose of V114 or Pevnar 13™). Descriptive summaries of AEs following administration of PNEUMOVAX™ will include NSAEs within 14 days of vaccination and SAEs/special events of interest occurring Month 12 after allo-HSCT (Day 1 relative to vaccination with PNEUMOVAX™23) through Month 13 after allo-HSCT (Day 30 relative to vaccination with PNEUMOVAX™23). Descriptive summaries of AEs following administration of a 4th dose of V114 or Pevnar 13™ will include NSAEs within 14 days of vaccination and SAEs/special events of interest occurring Month 12 after allo-HSCT (Day 1 relative to vaccination with a 4th dose of V114 or Pevnar 13™) through Month 13 after allo-HSCT (Day 30 relative to vaccination with a 4th dose of V114 or Pevnar 13™).

The rate of SAEs, vaccine-related SAEs and death that occur throughout the entire study follow-up period will also be summarized per 1000 person-years of follow-up by vaccination group.

In addition, the proportion of participants who have new onset and/or worsening of GVHD as well as relapse and progression of the underlying disease (ie, the disease for which the allo-HSCT was performed [see inclusion criterion 2 in Section 5.1]) during study participation will be summarized descriptively. Limited summaries may also be generated following each of the 3 doses of vaccination of V114 or Pevnar 13™.

Safety analyses will be based on observed data (ie, no imputation of missing data).

Table 6 Analysis Strategy for Safety Parameters

Safety Endpoint	95% CI for Within-Group Comparison	Descriptive Statistics
Injection-site redness/erythema (Days 1 to 5 for adult participants and Day 1 to Day 14 for pediatric participants) [†]	X	X

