Injection-site swelling (Days 1 to 5 for adult participants and Day 1 to Day 14 for pediatric participants) [†]	X	X
Injection-site tenderness/pain (Days 1 to 5 for adult participants and Day 1 to Day 14 for pediatric participants) [†]	X	X
Injection-site hard lump/induration for pediatric participants (Days 1 to 14) [†]	X	X
Muscle pain/myalgia (Days 1 to 14) [†]	X	X
Joint pain/arthralgia (Days 1 to 14) [†]	X	X
Headache (Days 1 to 14) [†]	X	X
Tiredness/fatigue (Days 1 to 14) [†]	X	X
Hives or welts/urticarial for pediatric participants (Days 1 to 14) [†]	X	X
Any AE [‡]	X	X
Any vaccine-related AE [‡]	X	X
Any SAE [‡]	X	X
Any vaccine-related SAE [‡]	X	X
Discontinuation due to AE [‡]	X	X
Death [‡]	X	X
Maximum temperature measurements meeting the Brighton Collaboration cut points (Days 1 to 5 for adult participants and Day 1 to Day 7 for pediatric participants)	X	X
Specific AEs by SOCs and PT		X
[†] Includes solicited events only. [‡] These endpoints are broad adverse event categories. For example, descriptive statistics for the safety endpoint of “Any AE” will provide the number and percentage of participants with at least 1 AE. AE = adverse event; CI = confidence interval; PT = preferred term; SAE = serious adverse event; SOC = System Organ Class; X = results will be provided.		

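### GVHD and relapse/progression are summarized as crude proportions over a follow-up whose length depends on chronic GVHD, with no confidence interval and no Table 6 row

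*Combined protocol and SAP*

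**What the plan says.** Section 8.4.8 states that new onset or worsening of GVHD since Day 1, and relapse or progression of the disease that led to transplant, "will be recorded as specific events of interest". Section 8.4.7 adds: "There are no events of clinical interest for this study". No other events are singled out in this way.

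Section 9.6.2 treats safety parameters at different levels:

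- Solicited AEs get within-group 95% CIs "based on the exact binomial method proposed by Clopper and Pearson". The broad AE categories are handled in the same manner, and maximum temperature also gets within-group 95% CIs.
- For the rest, "Point estimates by vaccination group will be provided for all other safety parameters (specific AE terms and system organ class terms").
- GVHD and relapse/progression have their own sentence: the proportion of participants with them "during study participation will be summarized descriptively".
- Person-time is used for a short list only: "The rate of SAEs, vaccine-related SAEs and death that occur throughout the entire study follow-up period will also be summarized per 1000 person-years".

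Table 6 separates a column headed "95% CI for Within-Group Comparison" from a column for descriptive statistics. Its last row, "Specific AEs by SOCs and PT", has only the descriptive column marked. Neither GVHD nor relapse/progression has a row.

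The same section also counts these events in the AE summaries for each vaccination period. Those windows are Day 1 to Month 12 after transplant for the three-dose series, and Month 12 to Month 13 after PNEUMOVAX 23 or a fourth dose.

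**The concern.** These are the safety outcomes most particular to allo-HSCT recipients, and section 8.4.1 requires them to be reported throughout participation. Yet headache gets an interval and GVHD does not.

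The summary over all of participation is also hard to interpret, because participation is not the same length for everyone and its length depends on chronic GVHD status, which overlaps with one of the events being counted. A participant who dies or leaves before an event has no defined handling. If such participants simply stay in the denominator, they count as non-events for time in which they were not observed. A reader of the report would see two percentages with no planned statement of their precision and no common horizon.

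**Working it through.** **1. Is a CI implied by the word descriptive?** In Table 5 (immunogenicity), descriptive statistics are expressly said to comprise an estimate and a 95% CI. In Table 6 the CI and the descriptive statistics are separate columns, and the text limits parameters outside the listed ones to point estimates. Section 9.4.2 does not list these events as safety endpoints either. No CI is the better reading; one sentence would settle it.

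**2. Length of observation.** Inputs from the Schedule of Activities: Visit 2 at 90 to 180 days after transplant; Visit 6 at 335 to 395 days after transplant; Visit 7 at 30 to 44 days after Visit 6; final phone contact at 166 to 194 days after Visit 6, for recipients of V114 or Prevnar 13 at Visit 6 only (participants with chronic GVHD).

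- Day 1 to Visit 6: 335 − 180 = 155 days at the shortest, 395 − 90 = 305 at the longest.
- Day 1 to end, PNEUMOVAX 23 at Visit 6: 155 + 30 = 185 to 305 + 44 = 349 days.
- Day 1 to end, fourth dose at Visit 6: 155 + 166 = 321 to 305 + 194 = 499 days.
- Extra planned time after Visit 6 for fourth-dose recipients: 166 − 44 = 122 to 194 − 30 = 164 days.

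The per-period AE summary after a fourth dose stops at Day 30. Later GVHD or relapse in these participants therefore enters only the whole-participation proportion (and the SAE person-year rate, if serious). Participants given PNEUMOVAX 23 have no planned contact over that stretch.

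**3. The plan's own precision figures.** Section 9.9.2 gives precision for SAEs only. For 125 V114 adults:

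- 80% chance of at least one event: 1 − 0.2^(1/125) = 1.28% (plan: 1.3%).
- 50% chance: 1 − 0.5^(1/125) = 0.553%, or 1 in 181 (plan: 0.6%, 1 in 182).
- Upper limit with no events: 1 − 0.025^(1/125) = 2.91% (plan: 2.9%).

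These reproduce within rounding. There is no counterpart for GVHD or relapse.

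**4. Precision for these events.** The documents give no background rate, so the rates below are assumptions. The Clopper-Pearson limits are the 2.5% quantile of Beta(x, n − x + 1) and the 97.5% quantile of Beta(x + 1, n − x).

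| Group | Assumed events | Exact 95% CI |
|---|---|---|
| Adults, one arm | 12/125 | 5.1% to 16.2% |
| Adults, one arm | 38/125 | 22.5% to 39.3% |
| Adults, one arm | 50/125 | 31.3% to 49.1% |
| Pediatric, one arm | 8/25 | 14.9% to 53.5% |

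If a difference between arms were shown, its 95% half-width at equal rates p and 125 per arm is 1.96 × √(2p(1 − p)/125):

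- p = 0.10: 1.96 × √0.00144 = 7.4 points
- p = 0.30: 1.96 × √0.00336 = 11.4 points
- p = 0.40: 1.96 × √0.00384 = 12.1 points

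Miettinen-Nurminen limits with 12, 38 and 50 events of 125 in both arms agree: 7.7, 11.4 and 12.1 points.

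**The case against.** The strongest reply is that this is an estimation study (section 9.3) whose safety objectives in section 3 are within each vaccination group. GVHD and relapse are not endpoints of any stated objective, so it is natural that intervals go to the solicited AEs and broad categories. Serious GVHD or relapse also enters the SAE row, with a CI and a person-year rate. Deaths are reported by arm in both ways. An unblinded external DMC reviews safety. All of this stands, but the SAE row pools these events with every other SAE, and none of it supplies an interval for the two events themselves.

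Four stronger readings are tempting, and the documents do not support them:

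- *The trial cannot say what V114 excess it could exclude.* It does not plan to, which is different. Counts and arm sizes would let anyone compute the interval. No safety endpoint has a planned between-group comparison, so this is not peculiar to GVHD. A marked Table 6 row would give a within-group CI and would not bound an excess either.
- *There is no time horizon for these events.* The per-period AE summaries have one, Day 1 to Month 12 and Month 12 to 13. It is missing only for the separate proportion over all participation.
- *The uneven follow-up biases the comparison.* Allocation is 1:1, stratified and blinded, so variation before Visit 6 should be balanced between arms. After Visit 6, observation time would differ by arm only if chronic GVHD did.
- *The plan counts early deaths and withdrawals as event-free.* The text says only that observed data are used without imputation. That they fall into the denominator as non-events is an inference from the use of a simple proportion.

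**Conclusion.** The point holds as an inexpensive improvement in how two designated events are summarized. The plan gives them no CI and no Table 6 row. The whole-participation proportion mixes planned follow-up of 185 to 349 days with 321 to 499 days according to the Visit 6 vaccine, and has no rule for death or withdrawal before an event. The uneven horizon affects interpretation of the proportion in each group; no bias between vaccines has been shown.

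The follow-up figures are the extremes of the visit windows, assuming on-schedule visits. The precision figures (22.5% to 39.3% for 38/125; difference half-widths of about 7 to 12 points for rates of 10% to 40%) assume event rates and 125 evaluable adults per arm, as section 9.9.2 does. They illustrate what a planned interval would show; they do not predict results. The supplemental SAP is not available here. In this text it is assigned exploratory methods, subgroup details and later changes, so it cannot be assumed to cover this.

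**What to change.** In Table 6, add two rows, one for new onset or worsening of GVHD and one for relapse or progression, with the within-group 95% CI column marked.

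In section 9.6.2, replace the whole-participation summary with a cumulative incidence of each event by vaccination group, from Day 1 to just before the Visit 6 vaccination. This reuses the plan's own first safety window and ends before follow-up diverges. Specify death as a competing event, censoring at last contact if earlier, and 95% CIs. Because that window still varies, state the day at which the curve is read; 155 days is the shortest scheduled interval from Day 1 to Visit 6. State that the cumulative incidence is the main summary and the crude proportion with exact CI is supportive, so that the two are not read as rivals.

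A V114 minus Prevnar 13 difference with CI is optional. If shown, label it descriptive and unadjusted, since no other safety endpoint has one. Events after Visit 6 can stay in the existing per-period summaries, with those beyond Month 13 listed separately for fourth-dose recipients.

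The cost is two table rows and one extra table, with no new visits, tests or participants. It needs onset and last-contact dates. Onset dates for worsening GVHD may be imprecise: the Schedule of Activities has no separate GVHD assessment, and GVHD grading at entry follows each institution's own scale.

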9.6.3 Demographic and Baseline Characteristics

The comparability of the vaccination groups for each relevant demographic and baseline characteristic will be assessed by the use of summary tables. No statistical hypothesis tests will be performed on these characteristics. The number and percentage of participants screened and randomized and the primary reasons for screening failure and discontinuation will be displayed. Demographic variables (eg, age, race, and gender), baseline characteristics,

prior and concomitant vaccinations and therapies will be summarized by vaccination group either by descriptive statistics or categorical tables.

9.7 Interim Analyses

A periodic review of safety and tolerability data across the V114 Phase 3 program will be conducted by an independent, unblinded, external DMC. A description of the structure, function, and guidelines for decision-making by the DMC, along with the timing and content of the safety reviews will be outlined in the DMC charter. Information regarding the composition of the DMC is provided in Appendix 1. There are no plans to conduct an interim analysis of unblinded immunogenicity data in this study. However, unblinded immunogenicity data will be made available to the DMC upon request to enable a benefit-risk assessment.

Study enrollment is likely to be ongoing at the time of any interim analyses. Blinding to intervention assignment will be maintained at all investigational sites. The results of interim analyses will not be shared with the investigators prior to the completion of the study. Participant-level unblinding will be restricted to an external unblinded statistician performing the interim analysis.

The DMC will serve as the primary reviewer of the results of the safety interim analyses and will make recommendations for discontinuation of the study or protocol modifications to an Executive Oversight Committee of the Sponsor (see Appendix 1 for details on the Committees Structure for this study). If the DMC recommends modifications to the design of the protocol or discontinuation of the study, this Executive Oversight Committee (and potentially other limited Sponsor personnel) may be unblinded to results at the intervention level in order to act on these recommendations. The extent to which individuals are unblinded with respect to results of interim analyses will be documented by the unblinded statistician. Additional logistical details will be provided in the DMC Charter.

Intervention-level results from the safety interim analysis will be provided by the unblinded statistician to the DMC. Prior to final study unblinding, the unblinded statistician will not be involved in any discussions regarding modifications to the protocol, statistical methods, identification of protocol deviations, or data validation efforts after the interim analyses.

9.8 Multiplicity

No adjustment will be made for multiplicity.

9.9 Sample Size and Power Calculations

9.9.1 Sample Size and Power for Immunogenicity Analyses

This is a descriptive study. This study will randomize approximately 150 participants into the V114 group and 150 participants into the Prevnar 13™ group. It is assumed that approximately 105 participants per vaccination group will be evaluable for PP immunogenicity analyses at Day 90 (based on a 70% evaluability rate).

The width of the within-group 95% CIs for the serotype-specific IgG GMCs depend on the sample size, variability of the natural log concentrations, and the magnitude of the IgG GMC. In Table 7, 95% CIs for various hypothetical Day 90 IgG GMCs and various hypothetical standard deviation estimates for the natural log titers are displayed.

Table 7 Within-Group 95% CIs for Varying Hypothetical IgG GMCs and Varying Standard Deviations with 105 Evaluable Participants in Each Vaccination Group

Standard Deviation of natural log titers†	Serotype-specific IgG GMC†		
	1	5	10
1.0	(0.83, 1.21)	(4.13, 6.05)	(8.26, 12.10)
1.5	(0.75, 1.33)	(3.75, 6.66)	(7.51, 13.32)
2.0	(0.68, 1.47)	(3.41, 7.33)	(6.82, 14.66)

†The estimates of the standard deviation, GMT and GMC are representative of those observed in V114-006.
 CI=Confidence Interval; GMC= Geometric Mean Concentration; IgG= Immunoglobulin G.

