9.3 Hypotheses/Estimation

Objectives of the study are stated in Section 3. This is an estimation study and no formal hypothesis testing will be performed.

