9.6.1 Statistical Methods for Immunogenicity Analyses

This section describes the statistical methods that address the primary and secondary immunogenicity objectives. Methods related to exploratory objectives will be described in the supplemental statistical analysis plan.

Immunogenicity analyses will be conducted for each of the 15 pneumococcal serotypes in V114 separately. To address the primary immunogenicity objective, evaluation of the IgG GMCs at 30 days following the 3rd dose of V114 and Prevnar 13TM (Day 90) will include descriptive summaries and within-group 95% CIs to be calculated for each vaccination group. Point estimates for the IgG GMCs will be calculated by exponentiating the estimates of the mean of the natural log values. The within-group CIs will be derived by exponentiating the CIs of the mean of the natural log values based on the t-distribution.

A similar statistical approach will be used to evaluate the OPA responses at 30 days following the 3rd dose of V114 and Prevnar 13TM (Day 90).

Descriptive statistics with point estimates and within-group 95% CIs will be provided for all other immunogenicity endpoints. For the continuous endpoints, a similar statistical approach will be used as described above for the primary endpoint. Point estimates will be calculated by exponentiating the estimates of the mean of the natural log values and the within-group CIs will be derived by exponentiating the CIs of the mean of the natural log values based on the t-distribution. For the dichotomous endpoints, the within-group CIs will be calculated based on the exact method proposed by Clopper and Pearson [Clopper, C. J. and Pearson, E. S. 1934].

Reverse Cumulative Distribution Curves for IgG concentrations and OPA titers will be graphically displayed by serotype at Day 90. A detailed analysis strategy for immunogenicity endpoints is listed in [Table 5](#).

Table 5 Analysis Strategy for Immunogenicity Variables

Endpoint/Variable (Description, Time Point)	Primary vs. Supportive Approach†	Statistical Method	Analysis Population	Missing Data Approach
Primary Endpoints				
IgG GMCs at Day 90	P	Descriptive Statistics (estimate, 95% CI)	PP	Missing data will not be imputed
	S		FAS	
Secondary Endpoints				
OPA GMTs at Day 90	P	Descriptive Statistics (estimate, 95% CI)	PP	Missing data will not be imputed

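### Table 7 uses an unstated normal quantile where Section 9.6.1 prescribes t-based intervals, so its planning intervals are about 1.2% too narrow on the log scale; one limit is also misrounded

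*Combined protocol and SAP*

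**What the plan says.** Section 9.6.1 sets the interval method for the primary immunogenicity endpoint, the serotype-specific IgG GMCs at Day 90: "The within-group CIs will be derived by exponentiating the CIs of the mean of the natural log values based on the t-distribution". The same rule is carried over to OPA at Day 90 and to the other continuous immunogenicity endpoints. No normal-approximation alternative is offered.

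Section 9.9.1 plans to randomize "approximately 150 participants into the V114 group and 150 participants into the Prevnar 13™ group" and assumes that "approximately 105 participants per vaccination group will be evaluable for PP immunogenicity analyses at Day 90", "based on a 70% evaluability rate". It then introduces Table 7 as showing "95% CIs for various hypothetical Day 90 IgG GMCs and various hypothetical standard deviation estimates". The table, titled "Within-Group 95% CIs for Varying Hypothetical IgG GMCs and Varying Standard Deviations with 105 Evaluable Participants in Each Vaccination Group", gives nine intervals, for log-scale SDs of 1.0, 1.5 and 2.0 and GMCs of 1, 5 and 10. The section does not name the quantile. The table's only footnote on its figures concerns the source of the SD and GMC values.

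Section 9.3 states: "This is an estimation study and no formal hypothesis testing will be performed". There is accordingly no power calculation, and the summary in Section 9.1 sends the reader to Section 9.9.1 for the expected variability of the GMCs at this sample size.

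**The concern.** In an estimation study, the expected interval width does the job that power does in a testing study. Table 7 is the only quantitative precision statement for the primary IgG endpoint. A reader who takes the table's inputs and applies the method in Section 9.6.1 should be able to reproduce it, and cannot. All the differences run one way: the table is slightly more favourable than the planned method would give at the same n and SD. What is at stake is whether a stated planning figure agrees with the stated method; the trial's results are not at issue.

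**Working it through.** **Inputs**
- Evaluable n per group: 150 × 0.70 = 105 (Section 9.9.1), so n − 1 = 104 degrees of freedom.
- SD of the natural log values: 1.0, 1.5, 2.0. GMC: 1, 5, 10 (Table 7).
- Confidence level: 95%, two-sided, within group (Table 7 title).
- Method: t-based interval for the mean log, exponentiated (Section 9.6.1).

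**Formula.** Limits = GMC × exp(± q × SD / √105), with √105 = 10.247.

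**Step 1: reproduce the table.** Take q = 1.95996 (normal).
- SD 2.0, GMC 10: 1.95996 × 2 / 10.247 = 0.3825, giving 10 × exp(±0.3825) = (6.82, 14.66). This is as printed.
- SD 1.0, GMC 10: 1.95996 × 1 / 10.247 = 0.1913, giving (8.259, 12.108), which rounds to (8.26, 12.11). The printed interval is (8.26, 12.10).
- Over all nine cells, 17 of 18 limits match to two decimals. The exception is 12.10. It equals 2 × 6.05, the rounded limit in the neighbouring cell, which suggests scaling from a rounded value.

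**Step 2: apply the Section 9.6.1 rule.** Take q = t(0.975, 104) = 1.98304.
- SD 2.0, GMC 10: 1.98304 × 2 / 10.247 = 0.3870, giving (6.79, 14.73).

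| SD | GMC | Printed | t, 104 df |
|---|---|---|---|
| 1.0 | 1 | (0.83, 1.21) | (0.82, 1.21) |
| 1.0 | 5 | (4.13, 6.05) | (4.12, 6.07) |
| 1.0 | 10 | (8.26, 12.10) | (8.24, 12.14) |
| 1.5 | 1 | (0.75, 1.33) | (0.75, 1.34) |
| 1.5 | 5 | (3.75, 6.66) | (3.74, 6.68) |
| 1.5 | 10 | (7.51, 13.32) | (7.48, 13.37) |
| 2.0 | 1 | (0.68, 1.47) | (0.68, 1.47) |
| 2.0 | 5 | (3.41, 7.33) | (3.40, 7.36) |
| 2.0 | 10 | (6.82, 14.66) | (6.79, 14.73) |

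Only 4 of the 18 limits agree, all of them at GMC 1.

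**Step 3: could another calculation explain the table?** With 12.10 set aside, the rounding of the other 17 limits confines q to between 1.9582 and 1.9607. That range contains 1.95996 and excludes 1.98304. At n = 105, t with 105 df matches 4 limits, t with 208 df (both groups pooled) matches 6, and q = 2 matches 2. For n from 100 to 111, the best t-based match is 12 of 18 (n = 108), and the best normal match at any n other than 105 is 8 of 18.

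**Step 4: size.** The ratio of log half-widths is 1.98304 / 1.95996 = 1.0118, about 1.2%. The largest change in any limit is 14.73 − 14.66 = 0.07.

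**The case against.** The strongest reply is that the two sections do different jobs. Section 9.6.1 governs the analysis of trial data; Table 7 is a planning illustration with hypothetical inputs and never claims to use the Section 9.6.1 formula. Normal approximations in planning tables are routine.

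The difference is also smaller than the looseness of the inputs. The 105 is approximate and rests on an assumed evaluability rate. For SD 2.0 and GMC 10, the t rule gives an upper limit of 14.67 at n = 107 and 14.64 at n = 108, so the discrepancy is worth about 2 to 3 participants per group. At n = 100 the limit would be 14.87, a larger move than the one at issue. The doubling of the SD across the table swamps a 1.2% effect. That 14 of 18 limits differ is a count of small shifts, 11 of them 0.03 or less.

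Most of this stands, and it fixes the point as minor. Two things survive it. The approximation is not disclosed, although the only method that the plan gives for these intervals is the t-based one. And the approximation does not explain 12.10, which is wrong under either quantile.

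A reader might go further and infer that the trial's reported intervals will fall short of 95% coverage. The documents do not support that: no reported interval will be built with 1.960, because Section 9.6.1 prescribes t for all of them.

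**Conclusion.** The point holds as a small inconsistency in a stated figure. At n = 105, Table 7 understates the log half-width by about 1.2% relative to the method in Section 9.6.1, and one of its limits is misrounded by 0.01.

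Use of the normal quantile is inferred from the numbers, since the plan does not name one, but the match leaves little doubt. The restated values rest on the table's own n, SDs and GMCs, and on n − 1 degrees of freedom.

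A reader might also infer that the sample size is inadequate or was set on a wrong figure. That does not follow. The plan sets no precision target, margin or decision rule against Table 7, and a judgement of adequacy would be the same on (6.82, 14.66) as on (6.79, 14.73).

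**What to change.** Restate Table 7 with t(0.975, 104) = 1.983:
- SD 1.0: (0.82, 1.21), (4.12, 6.07), (8.24, 12.14)
- SD 1.5: (0.75, 1.34), (3.74, 6.68), (7.48, 13.37)
- SD 2.0: (0.68, 1.47), (3.40, 7.36), (6.79, 14.73)

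The minimum alternative is a footnote saying that the table uses the normal approximation, together with the correction of 12.10 to 12.11. Either is an edit to one table. The full restatement makes the stated precision slightly less favourable; neither option touches the sample size, the analysis or study conduct. The change can wait for the next amendment made for other reasons.
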